4. PATIENT ELIGIBILITY

a. INCLUSION:

- i. Patients with a pathologic diagnosis of malignancy
- ii. Patients with any radiographic evidence of bone metastases, including plain x-ray, bone scan, CT scan, MRI, or PET scan
- iii. Patients with pain or dysaesthesia
- iv. Patients with a life expectancy of more than 3 months
- v. Patients able to complete pain assessment and quality of life surveys
- vi. Patients with multiple osseous sites are eligible; however should not treat more than 3 separate radiation treatment fields concurrently.
- vii. Patients with surgery for osseous metastases allowed.

b. EXCLUSION:

- i. Patients with prior radiation therapy to the treatment site
- ii. Patients with a current, untreated spinal cord compression
- iii. Patients with a radiographic or pathologic fracture to the treatment site
- iv. Patients with painful metastases to hands and feet that need to be radiated on protocol
- v. Patients previously treated with radioactive isotope (e.g. Sr89) within 30 days of randomization

5. PRE-TREATMENT EVALUATION:

- a. The workup will include physical examination, radiographic evidence of metastases with either x-ray, bone scan, CT scan or MRI, and pathologic confirmation of malignancy per MDACC standard of care.
- b. All eligible patients will be enrolled after completion of the eligibility checklist.
- c. Use of pain medications (narcotic/opioids/NSAIDs) will be evaluated.

6. TREATMENT PLAN:

- a. Patients will be randomized to receive radiation therapy to:
 - i. Arm 1: the standard hypofractionated regimen of 3 Gy x 10 fractions
 - ii. Arm 2: 12 Gy x 1 fraction or 16 Gy x 1 fractions adaptively depending on the size of the metastases or gross tumor volume (GTV).
- b. Patients will undergo CT simulation and either 2-D or 3-D treatment planning for radiation therapy.

- c. Patients can be treated with 2-D, 3-D, or intensity modulated radiation therapy (IMRT)
 - d. Patients will be treated with on board imaging (OBI) using KV, MV x-rays, cone beam CT or CT on rails per standard of care.
 - e. Patients will be treated with 4-20 MV photon beam, 5-20 MeV electron beam, or 200 MeV-300 MeV proton beam.
 - f. More than 1 osseous site may be included into one radiation treatment field.
7. EVALUATION DURING STUDY:
- a. All patients will be evaluated by the radiation oncologist during radiation treatment
 - b. If surgical intervention is necessary, the patients will be evaluated by the treating surgeon

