We will monitor the rate of radiation induced toxicity (skin dermatitis grade ≥ 4 , gastrointestinal (GI) grade ≥ 3 , genitourinary (GU) grade ≥ 3) by 12 months after the start of radiation therapy for the hypofractionated radiation therapy arm. We will enroll at least 25 patients and at most 105 patients on this treatment arm, and we will use the methods of Thall et al. (17, Thall et al.) to monitor the radiation induced toxicity rate.

We will stop enrolling patients on the hypofractionated radiation therapy arm if we have reason to believe that the rate of radiation induced toxicity for this arm is more than 10%.

We will actually monitor the time to radiation induced toxicity, because these toxicities may occur at any time from the start of radiation therapy. We will use the Clinical Trial Conduct website (<https://biostatistics.mdanderson.org/ClinicalTrialConduct>) to monitor the toxicity stopping rule. This website is built and maintained by the Department of Biostatistics. The research staff will be trained by the study statistician in the use of the website to monitor the stopping rules, with an emphasis on the importance of updating toxicity outcomes and follow-up dates.

To obtain the operating characteristics for the stopping rule we simulated the trial 1000 times for various scenarios described in the table below. We assumed that patients are enrolled at the rate of 5 per month on the hypofractionated radiation therapy arm, that we would follow patients for 12 months, and that we will evaluate the stopping rule continually. The table below summarizes the operating characteristics of this stopping rule.

Operating Characteristics for the Toxicity Monitoring Rule						
Median time to radiation induced toxicity (months)	12-Month Toxicity Rate	Pr(Stop Early)	Sample Size			Avg Trial Duration (Months)
			P ₂₅	Mean	P ₇₅	
120	0.07	< 0.001	105	105	105	33.2
60	0.13	0.113	105	103	105	32.8
40	0.19	0.667	77	89	105	30.1
30	0.24	0.949	60	73	85	26.9

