At any point in the trial time to radiation induced toxicity can be calculated for each patient, with the time interval regarded as censored at the date of last follow-up if toxicity has not been observed for a patient. We will apply a Bayesian method for updating prior information with time to toxicity data observed to that time. We assume that the time to toxicity for each patient is exponentially distributed with a median of λ_S months for the standard treatment and a median of λ_E for the experimental treatment. Given the historical data we assume λ_S follows an inverse gamma distribution with mean 78.95 months and a standard deviation of 0.15 months. The middle 95% of this distribution is between 78.66 and 79.24 months. These parameters correspond to a 12-month toxicity rate between 9.064% and 10.035%. We assume λ_E follows an inverse gamma distribution with a mean of 78.95 months and a standard deviation of 15.0 months. The middle 95% of this distribution is between 54.87 and 113.32 months. These parameters correspond to a 12-month toxicity rate between 7.077% and 14.066%.

Since the goal of the study is to achieve a toxicity rate of less than 10% at 12 months, the trial will be stopped early if, based on the available data, $\Pr(\lambda_E < \lambda_S \mid \text{data from the trial}) > 0.90$. This rule was chosen to achieve an approximately 0.10 early stopping probability if the true toxicity rate is 10%.

Final Analysis

We will use descriptive statistics to summarize the demographic and clinical characteristics of patients by treatment arm.

We will use the methods of Gooley et al. (18, Gooley) to estimate the cumulative incidence of treatment failure for each treatment arm with death as a competing event, and we will estimate the percent of patients without treatment failure at 3, 6, and 12 months for each treatment arm with a 90% confidence interval.

We will use the methods of Fine and Gray (19, Fine and Gray) to model time to treatment failure with death as a competing event and test the hypotheses stated above for phase II and for phase III. We will also estimate the hazard ratio for treatment with a 90% confidence interval.

For the 3 month pain response rate, the Cochran-Mantel-Haenszel test stratified by stratification factors at randomization will be used to test the difference between 2 treatment arms. Chi-squared test without adjusting for the stratification factors will also be performed as a secondary analysis.

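### The toxicity stopping-rule table matches a trial with no deaths, no losses and unbroken accrual, which is not the planned trial; it overstates protection if median survival is about 12 months or less

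*Combined protocol and SAP*

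**What the plan says.** All of this is in the combined protocol and SAP.

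- **Simulation (section 11, Toxicity Monitoring).** The sponsor reports "we simulated the trial 1000 times for various scenarios described in the table below". The assumptions are that "patients are enrolled at the rate of 5 per month on the hypofractionated radiation therapy arm", and "that we would follow patients for 12 months, and that we will evaluate the stopping rule continually". Arm size is bounded: "We will enroll at least 25 patients and at most 105 patients on this treatment arm". The printed Pr(Stop Early) is <0.001 / 0.113 / 0.667 / 0.949 for 12-month toxicity rates of 0.07 / 0.13 / 0.19 / 0.24.
- **Rule (same section).** "We assume that the time to toxicity for each patient is exponentially distributed". The median for the experimental arm "follows an inverse gamma distribution with a mean of 78.95 months and a standard deviation of 15.0 months". The median for the standard arm has the same mean and a standard deviation of 0.15, so it is in effect a constant. The arm stops when the posterior probability that the experimental median is the shorter exceeds 0.90.
- **Censoring in the actual monitoring (same section).** Time to toxicity is calculated "with the time interval regarded as censored at the date of last follow-up if toxicity has not been observed for a patient".
- **Population and follow-up.** Section 4 requires "Patients with a life expectancy of more than 3 months", and section 7 plans follow-up until death.
- **Accrual (section 11, Phase II).** Enrolment of 150 patients takes 15 months. Accrual is then suspended until 110 failures are seen, expected by month 22 at the latest.
- **Deaths elsewhere.** The Final Analysis text treats death as a competing event for treatment failure. The toxicity simulation mentions no deaths.

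**The concern.** The table is the plan's only evidence of how often the single-fraction arm would be stopped if toxicity were excessive. The prior for that arm is centred on the acceptable rate and carries the weight of about 30 events, so the posterior moves only as events build up. A patient who dies or is lost adds no further time and no further events. If the toxicity hazard is unchanged, the rule then has less to work with than the table supposes. The accrual suspension is also left out, and it acts in the opposite direction: patients already treated go on adding time while none are enrolled.

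A reader of the table sees roughly a two-in-three chance of stopping at 19% toxicity. The question is whether that figure describes the trial as planned.

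**Working it through.** **Inputs from the plan.** Prior mean 78.95 and SD 15.0 for the experimental median; standard median taken as 78.95; cut-off 0.90; 25 to 105 patients; 5 per month; true medians of 120, 60, 40 and 30 months. The 12-month rate is 1 − 2^(−12/median), which gives 0.067, 0.129, 0.188 and 0.242, as printed after rounding.

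**The rule.** For an inverse gamma prior:
- shape = 2 + (78.95/15)² = 29.70
- scale = 78.95 × (29.70 − 1) = 2266.1

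With d events and total exposure T, the posterior is inverse gamma (29.70 + d, 2266.1 + ln 2 × T). Stop if Pr(λ_E < 78.95) > 0.90.

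**Step 1: reproduce the printed table.** No deaths, no pause, a look at each enrolment from patient 25, exposure counted from entry to the look (10,000 runs):

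| 12-month rate | Printed Pr(stop) | Reproduced | Printed mean n | Reproduced |
|---|---|---|---|---|
| 0.07 | <0.001 | 0.0005 | 105 | 105.0 |
| 0.13 | 0.113 | 0.128 | 103 | 102.7 |
| 0.19 | 0.667 | 0.651 | 89 | 89.4 |
| 0.24 | 0.949 | 0.941 | 73 | 73.2 |

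The Monte Carlo standard error of the printed values, √(p(1−p)/1000), is 0.010, 0.015 and 0.007 in the last three rows. The differences are therefore 1 to 1.5 standard errors.

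The duration column agrees. Mean n/5 + 12 gives 33.0, 32.6, 29.8 and 26.6, against 33.2, 32.8, 30.1 and 26.9 printed. A 7-month pause would put the first row near 40. So the 12 months is time added after the last enrolment, and there is no pause in the table.

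**Step 2: censor exposure at death.** Deaths are exponential and independent of toxicity, and the toxicity hazard is unchanged. Median survival is an assumption. Accrual stays unbroken, as in the table.

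**Step 3: add the pause.** It comes after 15 × 5 = 75 patients on the arm and lasts 22 − 15 = 7 months.

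Pr(stop) at 13% / 19% / 24%:

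| Assumed median survival | Unbroken accrual | With 7-month pause |
|---|---|---|
| No deaths | 0.13 / 0.65 / 0.94 | 0.27 / 0.87 / 0.99 |
| 24 months | 0.09 / 0.52 / 0.88 | 0.15 / 0.71 / 0.96 |
| 18 months | 0.08 / 0.48 / 0.85 | 0.13 / 0.65 / 0.95 |
| 12 months | 0.06 / 0.41 / 0.79 | 0.10 / 0.55 / 0.89 |
| 6 months | 0.03 / 0.24 / 0.58 | 0.04 / 0.31 / 0.66 |
| *Printed* | *0.113 / 0.667 / 0.949* | |

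Separately coded runs agree to within about 0.03. The 0.07 row stays at about 0.001 or below throughout.

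**Step 4: enrolment at 19% toxicity.** The printed mean is 89. With unbroken accrual it becomes about 96 (12-month median survival) or 100 (6-month). With the pause it is about 90 or 98.

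**Step 5: what the rate means once patients die.** The crude 12-month rate is h_t/(h_t + h_d) × (1 − e^(−12(h_t + h_d))), where each hazard is ln 2/median. For the 19% row (toxicity median 40 months):
- 6-month survival: 0.1304 × (1 − 2^(−2.3)) = 0.104
- 12-month survival: 0.2308 × (1 − 2^(−1.3)) = 0.137

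A rate of 19% net of death is thus about 10% or 14% of patients actually having the toxicity. The plan does not say which rate the table shows.

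**The case against.** A reader might infer that the printed probabilities are simply too high, because patients need only be expected to live more than 3 months. The documents do not support that. The 3-month figure is an eligibility floor, not an expected survival, and no survival or loss figure appears anywhere. The plan's own accrual pause also raises the stopping probability. With it, the two effects roughly cancel at an 18-month median survival, and at 24 months the rule stops more often than printed. This part of the objection stands and makes the direction conditional.

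A reader might also infer from the wording that each patient was capped at 12 months of exposure. Without deaths, that gives 0.09 / 0.54 / 0.88 with looks during accrual, or 0.18 / 0.74 / 0.98 with looks continued through follow-up. Neither matches the print, so the missing element is censoring at death or loss.

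Three further points are fair:
- If toxicity arose early rather than at a constant hazard, deaths need not weaken the rule. With all 12-month toxicity spread evenly over the first 3 months (an assumption), unbroken accrual and a 6-month median survival, Pr(stop) rises from about 0.34 / 0.85 / 0.99 to 0.45 / 0.90 / 0.99. But the plan assumes exponential times, and the table is built on them.
- If the crude rate is what matters, less frequent stopping when fewer patients have the toxicity is not plainly lost protection. The plan has to say which rate it means.
- The rule itself handles censoring correctly, and 160 of 210 patients (about 80 of 105 on this arm) are already randomised. A new table bears on about 25 further patients on the arm. That limits the consequence but does not make the printed figures right.

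**Conclusion.** The concern holds in a conditional form. The table describes a trial with no deaths, no losses and unbroken accrual, and its stopping probabilities are not those of the trial as planned.

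Under the table's own accrual assumption, censoring at death lowers them in every row above 10% toxicity. At 19% the printed 0.667 becomes about 0.41 (12-month median survival) or 0.24 (6-month). With the planned 7-month pause the corresponding values are about 0.55 and 0.31. The shortfall has gone by about 18 months and is reversed at 24. The table therefore materially overstates protection only if median survival is about 12 months or less. The <0.001 row is not materially affected. The extra enrolment at 19% is small with the pause at a 12-month median (about 90 against 89) and larger at 6 months (about 98).

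These sizes rest on exponential toxicity and death times that are independent of each other, on assumed survival medians, and on a pause of the length the plan expects. The mismatch between table and plan needs none of the survival assumptions.

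**What to change.** Re-run the existing simulation with two changes: censor exposure at death or loss, and include the accrual suspension. Take survival and follow-up from the 160 patients already randomised, pooled over arms, so that no assumed median is needed. Replace the Pr(Stop Early), sample-size and duration columns. State beside the table the survival and loss assumption, the timing and length of the pause, and whether the 12-month toxicity rate is net of death or crude.

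The cost is one re-run and a replaced table, with no change to endpoints, arms or sample size. The downside is that less favourable stopping probabilities may be printed. No change to the 0.90 cut-off is proposed; altering a safety boundary mid-trial is a separate decision.

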where ρ is the hazard ratio (hypofractionated/standard) for time to treatment failure, as defined in section 1.0. A sample size of 150 patients (75 randomized to each treatment arm) will yield 90% power with a 1-sided significance level of 0.20 to reject the null hypothesis (H_0) and conclude that hypofractionated treatment is not inferior to standard treatment in terms of time to treatment failure. We use a 1-sided significance level of 0.20 as recommended by Rubinstein et al. (16, Rubinstein) for phase II screening trials. This sample size will yield 110 events (i.e., treatment failures). It will take 15 months to enroll all the patients, and the maximum study duration is expected to be 22 months to observe the 110 events. The final analysis for phase II will be performed once we've observed 110 events, and we will suspend accrual while we wait for these events to occur. We will continue to phase III only if we reject H_0 at the 0.20 significance level.

Phase III

The patients enrolled in the phase III part of the study will be included in the phase III part of the study. In the Phase II trial, we have already enrolled and randomized 160 patients, therefore we are requesting to enroll another additional 50 patients to reach a total of 210 patients. We will enroll another 50 patients in total of 210 patients (105 randomized to each treatment arm), after the rejection of the H_0 in the phase II part of the trial. The primary objective is to evaluate the pain response at 3 months by international pain consensus criteria after the additional 50 patients have been accrued, we will follow all patients for at least 3 months to assess the pain response. Assuming a 20% of the 3-month pain response rate for patients on MFRT arm, the 210 patients will ensure an 80% power to detect a 16% improvement in response rate (36%) with SBRT using a 1-sided 5% level test.

Pain response at 3 months is defined as reduction in pain score reported by MDASI at 2 points below baseline also taking into account narcotics use, as defined by International Pain Response Criteria.

This sample size calculation was performed using East 6 (Copyright © 2010, Cytel Inc., Cambridge, MA).

Toxicity Monitoring (phase II and phase III)

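### The toxicity rule is said to stop early with probability about 0.10 at a true 10% rate; the plan's own priors and table imply about 0.02

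*Combined protocol and SAP*

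**What the plan says.** All of this is in section 11 of the combined protocol and SAP, mainly under Toxicity Monitoring (phase II and phase III).

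- **Limit and action.** Enrolment on the hypofractionated arm stops if its toxicity rate is believed to exceed 10%. The goal is restated as a rate below 10% at 12 months.
- **Rule.** "the trial will be stopped early if, based on the available data", the posterior probability that the experimental median is shorter than the standard median exceeds 0.90.
- **Model.** Time to toxicity is exponential. The experimental median has an "inverse gamma distribution with a mean of 78.95 months and a standard deviation of 15.0 months". The standard median has the same mean with a standard deviation of 0.15 months, so it is in effect a constant.
- **Simulation.** There were 1000 simulated trials per scenario, with 25 to 105 patients on the arm and 5 enrolled per month. The plan assumed "that we would follow patients for 12 months, and that we will evaluate the stopping rule continually".
- **Table.** Early-stopping probabilities are < 0.001, 0.113, 0.667 and 0.949 at 12-month rates of 0.07, 0.13, 0.19 and 0.24 (medians 120, 60, 40 and 30 months).
- **Claimed calibration.** "This rule was chosen to achieve an approximately 0.10 early stopping probability if the true toxicity rate is 10" per cent.

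**The concern.** The sentence and the table are hard to hold together. If stopping had probability 0.10 at 10%, the curve would rise from under 0.001 to 0.10 between 7% and 10%, gain only 0.013 between 10% and 13%, and then gain 0.55 by 19%. A stopping probability that rises smoothly with the true rate does not do that.

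The sentence is the plan's only statement of how the safety rule behaves at its own limit, and the only reason given for the 0.90 cut-off. Someone overseeing safety would take it that the rule is roughly five times more likely to trigger at 10% than it is. The table cannot correct that impression directly because it has no 10% row.

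**Working it through.** **1. Priors.** For an inverse gamma, shape = (mean/SD)² + 2 and scale = mean × (shape − 1).

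- Shape = (78.95/15)² + 2 = 29.70. Scale = 78.95 × 28.70 = 2266.
- The central 95% interval is 54.87 to 113.32 months, or 12-month rates of 14.07% to 7.08%. This matches the plan.
- A median of 78.95 months gives 1 − 2^(−12/78.95) = 10.0%, so the prior is centred on the limit and carries the weight of about 30 events.

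**2. Posterior.** With d toxicities in T patient-months, the experimental median is inverse gamma with shape 29.70 + d and scale 2266 + T × ln 2. The rule stops when the posterior probability of a median below 78.95 months exceeds 0.90.

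**3. Look convention implied by the table.** Mean sample size ÷ 5 + 12 months gives 33.0, 32.6, 29.8 and 26.6. The printed mean durations are 33.2, 32.8, 30.1 and 26.9. So the table appears to count stopping during accrual and add 12 months of follow-up.

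**4. Reproducing the table.** Poisson accrual at 5 per month, first look at 25 patients, follow-up not capped, looks during accrual only:

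| Median (months) | Plan | Looks at each enrolment (6,000 runs) | Looks at each toxicity (20,000 runs) |
|---|---|---|---|
| 120 | < 0.001 | 0.000 | 0.0002 |
| 60 | 0.113 | 0.136 | 0.130 |
| 40 | 0.667 | 0.637 | 0.647 |
| 30 | 0.949 | 0.935 | 0.939 |

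With looks at each toxicity, the P25/mean/P75 sample sizes are 77/89/105 at 40 months and 60/73/85 at 30 months, identical to the plan.

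**5. The missing row.** The same settings at other true rates (the last column uses 10,000 runs):

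| True 12-month rate | Looks at each enrolment | Looks at each toxicity |
|---|---|---|
| 10% | 0.021 | 0.025 |
| 12% | 0.077 | 0.086 |
| 12.5% | 0.103 | 0.111 |
| 13% | 0.131 | 0.137 |

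Simulation noise cannot explain the gap. With 1000 runs and a true value of 0.021, the standard error is √(0.021 × 0.979/1000) = 0.0045.

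**6. Check from the printed table alone.** The two lowest rows are rates of 6.70% and 12.94%. Taking 0.001 for < 0.001, their probits are −3.090 and −1.211.

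- Linear in rate: the fraction is (10 − 6.70)/(12.94 − 6.70) = 0.53, so z = −2.10 and the probability is 0.018.
- Linear in log median: the fraction is ln(120/78.95)/ln 2 = 0.60, so z = −1.96 and the probability is 0.025.
- Logit interpolation gives 0.013. A straight line, which overstates a convex curve, gives about 0.06.

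**7. Other conventions.**

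| Convention | At 10% | At 13% |
|---|---|---|
| Follow-up capped at 12 months, looks during accrual | 0.014 | 0.09 |
| Capped, looks continued through follow-up | 0.035 | 0.16–0.18 |
| Uncapped, looks continued through follow-up | 0.066 | 0.38 |
| Accrual pause of 7 months after 80 patients | 0.035 | 0.22 |

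Repeat runs move the 10% figures slightly (0.012–0.016, 0.027–0.035 and 0.066–0.073 for the first three). The pause reflects the Phase II text, "we will suspend accrual while we wait for these events to occur". Its length is an assumption: 22 months maximum duration minus 15 months accrual. No variant reaches 0.10 at 10%.

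**8. A separate slip.** The standard-arm prior is said to correspond to a "12-month toxicity rate between 9.064% and 10.035" per cent. The lower bound should be 1 − 2^(−12/79.24) = 9.965%, not 9.064%. It does not affect the rule.

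**The case against.** **The replacement figure is not pinned down.** The plan does not say whether follow-up is capped or when looks end, and across conventions the value at 10% runs from about 0.01 to 0.07. With the planned accrual pause it is about 0.035, so 0.02 describes an uninterrupted trial. This stands, and it is why the corrected figure should come from the sponsor's own program under a stated convention.

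**The match to the table is not exact.** With 1000 sponsor runs the standard errors are about 0.010, 0.015 and 0.007 in the last three rows. With looks at each enrolment, the differences of 0.023, 0.030 and 0.014 are about two standard errors each. With looks at each toxicity they shrink to 0.017, 0.020 and 0.010, all within two. The exact convention remains unknown, but this uncertainty is far smaller than the gap between 0.02 and 0.10.

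**The 13% end of the crossing is weak.** Table-matching settings cross 0.10 at about 12.3–12.5%. Only the 12-month cap moves it to 13.0%, and the cap fits the table poorly (about 0.52 and 0.88 at medians of 40 and 30 months, against 0.667 and 0.949). So 12.5% is the better single figure.

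**The sentence triggers nothing.** The operative rule is the cut-off and priors, and an alert reader could suspect the mismatch from the table. This is true and limits the seriousness. It does not make the sentence correct, and nothing else in the plan describes the rule at 10%.

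The reading most favourable to the plan is uncapped follow-up with looks after accrual. It still falls short, gives 0.38 where the table prints 0.113, and does not suit a rule whose stated action is to stop enrolment.

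**Conclusion.** The concern holds. Under the plan's priors, cut-off, sample limits and accrual rate, early stopping at a true 10% rate has probability about 0.02, not about 0.10, and 0.10 is reached roughly 2.5 percentage points above the limit. The printed table alone shows only that the value at 10% should lie below 0.113. The figure of 0.02 also rests on the priors, exponential times, steady accrual of 5 per month, and looks during accrual, which is the convention the printed sample sizes and durations support. The conservatism comes from the prior's weight of about 30 events centred on 10% acting together with the 0.90 cut-off. The rule and the table remain usable, and no sample size or efficacy analysis is affected. The calibration statement is wrong and should be fixed.

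**What to change.** 1. Run the sponsor's simulation program at a median of 78.95 months and add the result to the table as a 10% row.
2. Correct the sentence to that result. About 0.02 is expected under the table's assumptions, against 0.113 already printed at 13%.
3. State the convention used: whether each patient's follow-up is capped at 12 months, and whether looks end when accrual ends.
4. Correct 9.064% to 9.965%.

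This costs one more simulated scenario and a few words, and the operating rule does not change.

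If the sponsor does intend 0.10 at 10%, that is a different and costlier decision, and it is the sponsor's to make. The cut-off or the prior would have to be recalibrated and the whole table re-simulated, including the accrual pause. To show the scale only, and not as a proposal: with uncapped follow-up, a cut-off near 0.82 gives 0.105 at 10% and 0.34 at 13%, and a prior standard deviation near 25 months gives 0.096 and 0.33. With a 12-month cap, both give about 0.08 at 10%. The Phase III text says "we have already enrolled and randomized 160 patients", about 80 of the planned 105 on this arm if allocation is equal. Recalibration would therefore move a safety boundary late in accrual, and a table built on steady enrolment of 5 per month would not describe it.
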